## List of Abbreviations

*This list should be modified to include protocol-specific terms.*

ACE-I	Angiotensin Converting Enzyme Inhibitor
AE	Adverse Event/Adverse Experience
AIDS	Acquired Immune Deficiency Syndrome
ARB	Angiotensin Receptor Blocker
ART	Antiretroviral Therapy
BMP	Basic Metabolic Panel
BP	Blood Pressure
CCC	Clinical Coordinating Center
CLIA	Clinical Laboratory Improvement Amendments
CONSORT	Consolidated Standards of Reporting Trials
CRF	Case Report Form
CVD	Cardiovascular Disease
DCC	Data and Coordinating Center
DM	Diabetes Mellitus
DSMB	Data and Safety Monitoring Board
ESPRIT	Evaluation of Subcutaneous Proleukin® in a Randomized International Trial
FDA	Food and Drug Administration
FRCn	Fibroblastic Reticular Cell Network
GCP	Good Clinical Practice
GFR	Glomerular Filtration Rate
HIPAA	Health Insurance Portability and Accountability Act
HIV	Human Immunodeficiency Virus
ICF	Informed Consent Form
IHC	Immunohistochemistry
IL-6	Interleukin-6
IND	Investigational New Drug
IRB	Institutional Review Board
LN	Lymph Node
LT	Lymphatic Tissue
N	Number (typically refers to participants)
NIA	National Institute of Aging, NIH
NIAID	National Institute of Allergy and Infectious Diseases
NIH	National Institutes of Health
OHRP	Office for Human Research Protections
OHSR	Office for Human Subjects Research
PBMC	Peripheral Blood Mononuclear Cells
PHI	Protected Health Information
PI	Principal Investigator
PK	Pharmacokinetics
QA	Quality Assurance
QIA	Quantitative Image Analysis
QC	Quality Control
SAE	Serious Adverse Event/Serious Adverse Experience
SD	Standard Deviation
SILCAAT	Subcutaneous, Recombinant, Human Interleukin-2 in HIV-Infected Patients with Low CD4+ Counts Under Active Antiretroviral Therapy
SMART	Strategic Management of Anti-Retroviral Therapy
TGF-β	Transforming growth factor-beta
TF	Tissue Factor

	Protocol Summary
Full Title	Losartan to reduce Inflammation and Fibrosis Endpoints in HIV
Short Title	LIFE-HIV
Clinical Trial Phase	Phase 2
IND Sponsor	NA
Conducted By	Minneapolis Medical Research Foundation and the University of Minnesota
Principal Investigator	[name], MS
Lead Statistician	[name]
Sample Size	110 participants
Study Population	HIV positive patients $\geq 50$ years on stable ART with HIV RNA level $\leq 200$ copies/mL, CD4+ count $\leq 600$ cells/mm  , and no indication for angiotensin receptor blocker (or ACE-inhibitor)
Accrual Period	Anticipated enrollment 1 year
Study Design	Randomize 110 participants 1:1 to receive losartan 100mg or matched placebo daily (double-blind).
Study Duration	12 months
Intervention	Losartan 100mg versus matching placebo taken daily
Primary Objective	To evaluate the effects of losartan on systemic inflammation, as reflected in plasma levels of IL-6
(Main) Secondary Objective	To evaluate the effects of losartan on immune recovery, as reflected in peripheral blood CD4+ T-cells
Additional Secondary Objectives	Evaluating the effects of losartan on monocyte and T-cell activation in blood, coagulation activation, recovery of T-cell subsets in blood, adherence, tolerability, durability of findings, and lymphatic tissue assessments (in a subset of $n \geq 30$ ) of fibrosis, cellular activation, and T-cell homeostasis

# Schematic of Study Design

## Statement of Compliance

This trial will be conducted in compliance with the protocol, International Conference on Harmonization Good Clinical Practice E6 (ICH-GCP), and the applicable regulatory requirements including U.S. Code of Federal Regulations applicable to clinical studies (45 CFR 46 and 21 CFR 50, 56 and 21 CFR 312), directive 2001/20/EC on the approximation of the laws, regulations and administrative provisions of the Member States relating to the implementation of good clinical practice in the conduct of clinical trials on medicinal products for human use as amended by Commission Directive 2005/28/EC and NIAID Clinical Terms of Award. All key personnel (all individuals responsible for the design and conduct of this study) have completed appropriate Human Subjects Protection Training.

# 1 INTRODUCTION

## 1.1 Background and Rationale

### Premise

Contemporary antiretroviral therapy (ART)-treated HIV-infected patients are at increased risk for cardiovascular disease (CVD), cancer, and other HIV-associated non-AIDS conditions. This excess risk is due to multiple factors, including a higher burden of traditional risk factors, persistent inflammation and sub-optimal immune recovery after starting ART. Independent of HIV infection, older age increases risk for non-AIDS conditions and is itself associated with greater inflammation, reduced immune recovery after starting ART, and declining immune function (so called immune senescence). Safe treatments that target this pathology, beyond HIV treatment with ART, represent a major unmet need for older HIV positive patients.

The LIFE-HIV trial is a critical step to advance this field, prior to conducting a clinical outcome trial, by testing the effects of losartan treatment in a translational clinical trial that will improve our understanding of non-AIDS disease pathogenesis. Ongoing inflammation contributes to excess CVD, cancer and disease in multiple organ systems. Specific to HIV pathogenesis, immune activation and associated inflammation also drives collagen deposition (i.e., fibrosis) in lymphatic tissue (LT), disrupting T-cell homeostasis and limiting immune recovery, which further increases non-AIDS risk. Losartan is a safe, inexpensive, medication with immunomodulatory and anti-fibrotic properties, quite apart from lowering blood pressure. We will test the hypothesis that losartan will reduce inflammation and improve tissue fibrosis leading to additional immunologic recovery. These treatment effects have been demonstrated in uninfected populations (e.g., those with renal or connective tissue diseases), but have not been tested among HIV positive patients where the mechanisms driving ongoing immune activation are somewhat unique to this disease.

### Scientific Background

The Changing Spectrum of Morbidity and Mortality Among HIV Positive Patients: Antiretroviral therapy (ART) effectively and durably suppresses HIV replication, leads to immune recovery (increasing CD4+ T-cell counts) and prolonged life expectancy, and has changed the spectrum of morbidity and mortality among HIV positive persons. Among well-treated patients with levels of HIV RNA below the level of detection, non-AIDS-related conditions are now a more common cause of morbidity and mortality than AIDS. The most relevant serious non-AIDS-related diseases in current clinical practice include atherosclerotic cardiovascular disease (CVD), cancer, liver disease, end-stage renal disease, bone disease and subclinical neurocognitive dysfunction. Of these, CVD and cancer constitute the vast majority of clinical events.

What Contributes to Persistent Inflammation in Persons with ART-treated HIV Infection? HIV treatment with ART reduces activation of the immune response, including levels of inflammatory cytokines, though most immunologic abnormalities persist compared to

HIV uninfected persons. The level of T-cell activation (e.g., CD38/HLA-DR expression), reflecting adaptive immunity, predicts risk for AIDS and has been associated with CVD risk in cross-sectional studies. More recent data demonstrate that innate immune activation also contributes to chronic inflammation. Activated monocytes (e.g., CD16+) are more frequent with HIV infection. The CD16+ monocyte subset may be preferentially infected by HIV, demonstrate greater production of cytokines, and is independently predictive of coronary artery calcium (CAC) among HIV+ patients.

The precise mechanisms driving high level immune activation are not entirely clear, but appear to involve both a persistent anti-HIV response (even with HIV RNA at low levels) and a more generalized immune activation (e.g., cytokine release). Potential factors specific to HIV infection that may account for excess inflammation include: a) destruction of gut epithelium, which leads to chronic translocation of bacterial products, b) dysregulated inflammatory responses to co-pathogens (e.g., cytomegalovirus), and c) loss of key regulatory response. Given that drivers of HIV-related inflammation are multi-factorial and diverse, a treatment that down regulates the inflammatory response more broadly irrespective of the cause, like losartan, may be more likely to show efficacy.

#### Pathologic Consequences of Ongoing Immune Activation For Immune Recovery:

An important pathologic consequence of persistent immune activation is fibrosis of lymph node (LN) structures necessary for T-cell homeostasis. Ongoing immune activation stimulates production of TGF- $\beta$  that leads to fibrotic changes in the parafollicular T-cell zone of lymph nodes. LN fibrosis damages the fibroblastic reticular cell network (FRCn) that forms the skeletal anatomy of the T-cell zone, produces IL-7, and directs movement of T-cells within the LN. The loss of naïve T-cells further perpetuates the process through declines in lymphotoxin- $\beta$  (from T-cells) that is essential for FRCn vitality. The vicious cycle leads to more reductions in IL-7 and T-cell depletion. LN collagen is therefore not only a cause of T-cell depletion but also contributes to incomplete immune recovery with ART via impaired survival of naïve T-cells. Losartan has been shown, both in vitro and in vivo, to inhibit TGF- $\beta$  and reverse existing fibrosis. These treatment effects may be particularly important for older HIV patients, given that normal aging leads to thymic involution and increased apoptosis, reducing circulating naïve T-cells.

#### Study Outcomes: IL-6 and CD4 count Predict Non-AIDS Risk:

Excess risk for non-AIDS conditions is due to multiple factors, including a higher burden of traditional risk factors, but persistent immune depletion and ongoing inflammation despite effective ART are key risk factors specific to HIV and are the focus of this trial. We have previously reported that CD4+ T-cell count, including changes after starting ART, predict risk for a composite of non-AIDS conditions (including CVD and cancer). Although risk for both AIDS and non-AIDS conditions decline with higher CD4+ counts, this is more drastic for AIDS events. Non-AIDS conditions are therefore much more common than AIDS events at moderate to higher (e.g., >500 cells/mm^3) CD4+ counts. Mechanisms differ between distinct non-AIDS conditions, but

associations between CD4+ count and risk for these conditions has been reproduced in multiple cohorts.

Recent data from a number of epidemiologic studies have shown that inflammatory biomarkers well validated in the aging and cardiovascular fields are elevated with untreated and (to a lesser degree) treated HIV infection, and predict risk for CVD, cancer, and non-AIDS mortality. Our group conducted a series of nested case-control and cohort studies, using data from 3 large HIV trials (SMART, ESPRIT, and SILCAAT), and determined that associations for risk of CVD, cancer, a composite of serious non-AIDS events, and all-cause mortality was most robust for levels of interleukin-6 (IL-6). These associations are not attenuated by adjusting for HIV or traditional CVD risk factors, are several-fold higher than reported in HIV-negative studies, and persist over a median of 5.5 years of follow-up, making it an ideal risk marker for a broad composite of non-AIDS conditions.

### **Rationale for Losartan**

Losartan has well-established off-target, or non-blood pressure lowering, effects that may benefit HIV positive patients. Angiotensin-2 (AT-2), a potent vasoconstrictor, is a key regulator of the renin-angiotensin-aldosterone system (RAAS) that is also pro-inflammatory (through Nuclear Factor-Kappa B [NF-κB] pathways) and pro-fibrotic (via transforming growth factor beta [TGFβ1] induced connective tissue growth factor [CTGF] expression). ARBs (angiotensin receptor blockers) selectively block AT receptor-1, mitigating the consequences for inflammation and fibrosis, but importantly, have fewer side effects than ACE-I. Tolerability to losartan (100mg) is considered excellent, with self-reported side effects no different than for placebo in clinical trials.

There exists a large body of evidence that ARBs (e.g., losartan) down-regulate immune activation. Angiotensin-2 induces activity of NF-κB, a transcription factor that, in part, regulates immune activation and cytokine release (e.g., IL-6 and TNF-α). Numerous (HIV uninfected) studies of ARBs or ACE-Is demonstrate reductions in inflammatory markers (e.g., IL-6, TNF-α, and CRP) via mechanisms both related to and independent of angiotensin receptor blockade. In hemodialysis patients, losartan also decreased monocyte activation (CD16+) *in vivo* (to levels seen in healthy controls) and prevented monocyte activation (or CD16 expression) *in vitro*. In animal models, ARBs suppress transcription and release of IL-6 and other cytokines by monocytes.

Independent of reducing immune activation, losartan may improve T-cell homeostasis and immune recovery by reversing existing tissue fibrosis through a well characterized mechanism of blocking TGF-β at the level of phosphorylation of SMAD-2,3. In animal models (of vascular, renal and cardiac fibrosis), losartan therapy inhibits TGF-β activity and improves histologic abnormalities. In humans, losartan reduces urinary levels of TGF-β among those with transplant related kidney fibrosis, reversed fibrosis and improved in cardiac function among those with myocardial fibrosis. Losartan's net effect is also to shift the balance of matrix metalloproteases and their inhibitors in favor of tissue remodeling, which then reduces fibrosis.

Finally, the 100mg dose of losartan was chosen: a) to maximize the treatment effect on inflammation and fibrosis, b) due to the excellent safety profile and lack of difference in adverse events between 50mg and 100mg doses (data from 20 clinical trials), and c) due to the predictable CVD risk reduction through BP lowering.

## 1.2 Objectives

Our general goal is to evaluate the potential effectiveness of losartan (100mg daily) for reducing inflammation and improving immune recovery, given the potential for these treatment effects to reduce risk for long-term non-AIDS-defining complications among older HIV positive participants. Prior to conducting a clinical outcome trial, candidate treatments must be studied among HIV positive patients given the unique pathogenesis driving inflammation and disease risk. Study objectives then include:

- Primary Objective: Evaluate the treatment effects of losartan on systemic inflammation
- (Main) Secondary Objective: Evaluate the treatment effects of losartan on T-cell homeostasis and immune recovery of T-cell population

## 2 METHODOLOGY

### 2.1 Trial Design

The potential benefits of losartan (100mg daily) will be studied among HIV positive individuals over age 50 years whose CD4 counts remain  $\leq 600$  cells/mm^3. Participants (n=120, 60 per group) will be randomized to receive losartan or matching placebo daily. After randomization, participants will start losartan (or placebo) at a dose of 50mg once daily, increasing to 100mg once daily at the 2-week study visit pending results of a week 2 toxicity lab evaluation (see 2.4 below for criteria). Following month 1, participants will return for follow-up study visit procedures at months 3, 6, 9, and 12. A lymph node biopsy will also be performed at baseline and month 12 from a subset of participants (n $\geq$ 30).

Changes from baseline in measures of inflammation, immune activation, immune recovery and fibrosis within lymphatic tissues will be studied. The primary outcome will be the average of IL-6 levels over 12 months, and the main secondary outcome will be change in CD4 count in blood over 12 months.

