## 2.7 Sample Size Considerations

### Power for Reduced Inflammation (IL-6 levels)

- The primary analysis will compare baseline-adjusted log IL-6 measurements at 1, 3, 6, 9 and 12 months between treatment groups.
- Standard deviation (SD) data from SMART (n=122; baseline and month 1) and ESPRIT (n=147; baseline and month 12) on participants who were on continuous ART between both time points were used to estimate a log IL-6 SD of 0.74 pg/mL.
- We assumed a 28% reduction in IL-6 with losartan was plausible based on our pilot data and data from HIV negative studies in the general population.

Based on assumptions above, assuming 5% missing data, and considering the potential

clinical risk reduction associated with IL-6 changes of this magnitude (see epidemiologic data, following paragraph), a total sample size of n=110 will be enrolled. With this sample we will have 80% power to detect an absolute reduction of 0.3 log(IL-6), corresponding to a 26% reduction in IL-6, with a two-sided Type I error of 0.05.

Pooled data from 3,766 participants in SMART, ESPRIT and SILCAAT trials who were taking continuous ART with an HIV RNA level <400 copies/mL at entry—a group that resembles our target population—indicate that a 26% lower baseline IL-6 level is associated with a 34% lower risk of serious non-AIDS events or death from any cause.

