### **Power for Immune Recovery (CD4+ T-cell count)**

- The primary analysis will consider average changes in log10 blood CD4 levels (total and naïve) over 12 months. Total CD4 count will be measured at 1, 3, 6, 9, and 12 months, and 4 pre-treatment baseline values (2 historical within prior year, 1 screening, 1 baseline) will be averaged to compute baseline CD4+ count for analyses. Averaging multiple baseline measurements will reduce variability and thereby increase statistical power. The log10 naïve CD4+ subset count will be measured at baseline and months 6 and 12.
- Based on participants ≥ age 50 in the SMART and ESPRIT studies (n=510 total), the estimated SD of yearly changes in log10 total CD4+ count is 0.11. Based on preliminary data from [name] lab, the estimated SD of yearly changes in the log10 naïve CD4 subset is 0.24.

With our sample size of n=110, we estimate that we will have 80% power to detect a 9.6% (19.8%) difference in total (naïve) CD4 count. Assuming a baseline total CD4 level of ~300-400 cells/mm^3, a 9.6% increase in CD4 count corresponds to an approximate average annual increase of 30-40 cells per year. From our prior epidemiologic work studying clinical risk based on total CD4+ count in blood after treatment with ART, a difference in this range would correspond to 5-8% difference in risk for a composite of non-AIDS events.

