## **5.2 Frequency and Content of Data and Safety Monitoring**

To ensure compliance and data are reported correctly and completely, CRF data will be monitored monthly for completeness and compliance with the study protocol. Queries for clarification or data completion will be posted to a site-specific and password protected section of the LIFE-HIV website.

The PI will be informed of serious adverse events as soon as they occur and will notify the NIA and DSMB within 24 hours of notification. During the study the DSMB will meet at least yearly either in-person or by teleconference call to review study progress, data quality, and participant safety. An initial DSMB meeting will be scheduled as soon as any of the following occurs:

- i. Six months have elapsed since enrollment of the first patient
- ii. 50% of goal enrollment is achieved
- iii. 30 person-years of follow-up is achieved

The data and safety monitoring report will include data on: enrollment (including progress), visit attendance, completeness of data, completeness and quality of specimen collection, baseline characteristics, adherence and discontinuation of medication, and side effects and adverse events.

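### Section 2.1 randomises 120 participants (60 per group), but the Protocol Summary and Section 2.7 give 110

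*Combined protocol and SAP*

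**What the plan says.** Five places in the combined protocol and SAP give a total sample size.

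| Place | Total | Wording |
|---|---|---|
| Section 2.1, Trial Design | 120 | "Participants (n=120, 60 per group) will be randomized to receive losartan or matching placebo daily" |
| Protocol Summary, Sample Size row | 110 | "110 participants" |
| Protocol Summary, Study Design row | 110 | "Randomize 110 participants 1:1 to receive losartan 100mg or matched placebo daily (double-blind" |
| Section 2.7, IL-6 power | 110 | "a total sample size of n=110 will be enrolled" |
| Section 2.7, CD4 power | 110 | "With our sample size of n=110, we estimate that we will have 80% power" |

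Section 2.7 reaches its 110 after allowing for 5% missing data, with 80% power for a 0.3 log reduction in IL-6 "with a two-sided Type I error of 0.05". Section 5.2 makes one of three alternative triggers for the first DSMB meeting depend on the target: "50% of goal enrollment is achieved".

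**The concern.** The number to be randomised is a basic design figure and should have one value. Section 2.1 and the Study Design row both describe randomising participants 1:1 to losartan or placebo, so they count the same thing and cannot both be right. Because Section 2.1 also gives 60 per group, 120 does not look like a single mistyped digit.

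Three things depend on the number:

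- **End of accrual.** If 110 is meant, Section 2.1 has sites randomise 10 people beyond the number that Section 2.7 justifies. If 120 is meant, neither power statement describes the trial to be run.
- **DSMB oversight.** The half-enrolment trigger needs one denominator, and so does the recruitment and accrual review that Section 5.5 assigns to the board.
- **Reporting.** A final count of 110 or of 120 could each be called on target or off target.

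**Working it through.** **1. Can the documents' own allowances link 110 and 120?**

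Inputs: totals of 110 and 120 as listed above; 5% missing data (Section 2.7).

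- Inflating 110 for 5% missing: 110 / 0.95 = 115.8, so 116.
- Deflating 120 by 5%: 120 × 0.95 = 114.
- Loss needed to turn 120 into 110: 1 − 110/120 = 8.3%. The documents give no such figure.

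Section 2.7 has in any case already applied the 5% in arriving at 110. Section 4.6 on withdrawal has no replacement rule. Under Section 2.6, a participant whose baseline biopsy fails can still be randomised into the main study, so the lymph node substudy adds no separate group. No amendment note in the available text marks either figure as superseded.

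**2. Can the stated power show which total is right?**

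Inputs from Section 2.7: difference 0.3 log (1 − exp(−0.3) = 25.9%, matching the stated 26%), SD 0.74, two-sided alpha 0.05, 5% missing.

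A plain two-sample comparison, normal approximation, has power Φ(0.3 / (0.74 × √(2/m)) − 1.960), where m is the evaluable number per group:

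- 110 enrolled, m = 55 × 0.95 = 52.25: 54.5%
- 120 enrolled, m = 60 × 0.95 = 57: 58.1%

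Neither gives 80%. Section 2.7 does not say whether 0.74 is the SD of a single level or of a change, and gives no within-person correlation. The result depends on what is assumed:

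| Reading of 0.74 (assumption) | Effective SD | Power at 110 | Power at 120 |
|---|---|---|---|
| SD of a change; mean of 5 follow-ups minus 1 baseline | 0.573 | 76.3% | 79.8% |
| SD of a change; mean of 5 follow-ups minus mean of 2 baselines | 0.438 | 93.9% | 95.5% |
| SD of a single level; baseline-adjusted, compound symmetry, correlation 0.3 to 0.8, 1 or 2 baselines | 0.27 to 0.44 | 93% or more | 95% or more |

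All rows include 5% missing. The first comes close to 80% at 120, but it uses one baseline value, whereas Section 6 averages two and adjusts for them. The power statement therefore does not settle which total was intended. The undefined SD is a separate point, and the inconsistency does not depend on it.

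**3. How much does the difference matter if the plan's 80% at 110 is taken as given?**

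Only the ratio of sample sizes is needed, with the same proportion missing at both.

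- Noncentrality at 110: 1.960 + 0.842 = 2.802.
- At 120: 2.802 × √(120/110) = 2.926. Power = Φ(2.926 − 1.960) = 83.3%.
- Detectable log IL-6: 0.300 × √(110/120) = 0.287. Reduction: 1 − exp(−0.287) = 25.0%, against 25.9%.
- Total CD4, as an increase on the log10 scale: log10(1.096) × √(110/120) = 0.0381, which is 9.2% against 9.6%.
- Naive CD4: log10(1.198) × √(110/120) = 0.0751, which is 18.9% against 19.8%.

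**4. The DSMB trigger**

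Half of the goal is 55 or 60. Section 5.2 calls the first meeting at the earliest of six months from first enrolment, half of goal enrolment, or 30 person-years. The Protocol Summary anticipates one year of enrolment. Assuming uniform accrual:

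- At 110 a year (9.17 a month), the 55th participant arrives at 55 / 9.17 = 6.0 months, when the calendar trigger fires anyway. At that rate or slower, the choice of total changes nothing.
- At 10 a month, 55 is reached at 5.5 months and 60 at 6.0 months, a delay of half a month. Faster accrual shortens this, since the gap is 5 participants.
- Person-years at 10 a month after t months are 10t²/24. Thirty is reached at t = √72 = 8.5 months, so this trigger does not come first.

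**The case against.** The strongest reply is that this is editorial. The one section that derives the sample size states 110, and both summary rows and the CD4 power statement agree. One parenthesis against four consistent statements reads as a leftover, and nobody would be misled about which number carries the power claim. No efficacy or futility boundary depends on the total, because Section 5.1 plans no formal interim analysis. The DSMB effect is at most about two weeks under uniform accrual, and the board receives enrolment and adverse-event reports every three months regardless. The rescaled power and detectable differences rest on an 80% figure that cannot be reproduced from the stated inputs. The CD4 figures have the same weakness: with SD 0.11 and 110 participants, a plain two-sample formula with no missing data gives a detectable difference of 0.059 log10 (about 14%), not 9.6%.

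Most of this stands. The weight of the text favours 110, the DSMB consequence is slight, and the rescaled figures only show what follows if the plan's own power statements are accepted. It does not remove the contradiction. Section 2.1 is the design section, it says how many will be randomised, and it gives a matching per-group number. That 120 is a leftover remains an inference, because the text never says so.

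**Conclusion.** The inconsistency is real and is in current text. Section 2.1 is 10 participants (5 per group) above the other four statements, and nothing in the documents reconciles them. This conclusion comes from reading the passages side by side and needs no assumption about variance or correlation.

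The consequences are modest. There is no threat to the validity of the analysis and no sign that this makes the trial underpowered: moving from 110 to 120 would raise power by about 3 percentage points, conditional on the stated 80% at 110. What is lost is a single, checkable target for accrual and for the DSMB. The correction is still worth making, because the planned size underlies both power statements and is cheap to put right.

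**What to change.** If 110 is the target, change Section 2.1 to 110 participants, 55 per group. This is a one-line correction and nothing else moves.

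If 120 is the target, change the Sample Size and Study Design rows of the Protocol Summary and both totals in Section 2.7, and recompute the IL-6 and CD4 power and detectable differences at 120 from the underlying variance assumptions, rather than by rescaling the present figures.

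In either case, give the half-enrolment trigger in Section 5.2 as a number (55 or 60), so that it does not depend on which section is read.
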